8.5.2.2. Estimator

8.5.2.2.1. Superiority Test

For a superiority test of each filgotinib group compared to the placebo group on a binary efficacy endpoint, a logistic regression analysis with treatment groups and stratification factors in the model will be used.

For a superiority test of each filgotinib group compared to the placebo group on a continuous efficacy endpoint that is longitudinally collected, a mixed-effect model repeated measures (MMRM) analysis with treatment groups and stratification factors as fixed effects and subjects as a random effect in the model will be used. The model may also include visit, treatment-by-visit interaction, and the continuous baseline value as fixed effects.

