Appendix 25. LDI: Leeds Dactylitis Index

Dactylitis has been defined as "uniform swelling such that the soft tissues between the metacarpophalangeal and proximal interphalangeal, proximal and distal interphalangeal, and/or distal interphalangeal joint and digital tuft are diffusely swollen to the extent that the actual joint swelling could no longer be independently recognised."⁽¹⁾ Dactylitis is a hallmark clinical feature in patients with spondyloarthropathies (SpA) and is commonly observed in psoriatic arthritis.

Dactylitis occurs in 16-48% of cases of psoriatic arthritis (PsA). Acute dactylitis has been shown to be a clinical indicator of disease severity in PsA; conversely, chronic, non-tender diffuse dactylitic swelling may be less clinically significant⁽²⁾. Dactylitis is due to inflammation in the majority of tissues in the digit - the tendon sheaths, joints, bones and soft-tissues in between⁽³⁾. Recurrent dactylitis, often in the same digit(s), may be the only clinical manifestation of PsA.

The only validated tool for assessing dactylitis is the Leeds Dactylometer⁽⁴⁾. The validity of this instrument has been assessed using the OMERACT filter. The instrument and tool have demonstrated good evidence of responsiveness in a clinical trial⁽⁵⁾. In addition, the instrument incorporates a definition of dactylitis (a 10% difference in the ratio of circumference of the affected digit to the contralateral digit). Using the contralateral digit as a normalizer enables any inter-individual variation in measurement technique to be minimised. The instrument comes with an assessment sheet (see reverse) which provides automatic computation of the Leeds Dactylitis Index.

How to use the Leeds Dactylometer

1. The fingers and toes are visually inspected by the examiner. Those digits which look dactylitic are measured.
2. Slip the loop of the Dactylometer around the base of the digit adjacent to the web space. Pull the indicator strip tight so that the base of the digit blanches slightly (see illustration). The collar of the device should be firmly pressed against the base of the digit, as illustrated.
3. Record the circumference in mm on the Dactylometer record sheet
4. Repeat the procedure on the contralateral digit
5. If both ipsilateral and contralateral digits are thought to be dactylitic then use the reference range (given at the foot of the sheet) as the comparator.

6. Only record the digits with a 10% difference in circumference

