For the superiority test of filgotinib 200 mg or filgotinib 100 mg group versus placebo control group in continuous key secondary endpoints such as the change from baseline in HAQ-DI at Week 12, the change from Baseline in SF-36v2 PCS at Week 16, the change from Baseline in LEI at Week 16 for subjects with enthesitis at Baseline, the change from Baseline in FACIT-Fatigue at Week 16 and the change from Baseline in LDI at Week 16 for subjects with dactylitis at Baseline, a mixed-effect model repeated measures (MMRM) analysis that includes data at postbaseline visits through Week 16 will be applied. Subjects that have a baseline value and at least 1 postbaseline value are included in the analysis. The MMRM models will be used to evaluate treatment effect on change score from Baseline, with baseline value, stratification factors, treatment, visit, and treatment by visit interaction included as fixed effects and subject being the random effect. The MMRM model will include all treatment groups. An unstructured variance-covariance matrix will be used. The Kenward-Roger method will be used to estimate the degrees of freedom. Missing data will not be otherwise imputed using the MMRM approach. The least squares (LS) means and 95% CIs of the difference in mean change from Baseline between each filgotinib dose group and placebo group from MMRM will be provided at all the visits in Main study including Week 12 and Week 16.

In case of limited data leading to improper use of MMRM model, the descriptive statistics (sample size, mean, SD, median, Q1, Q3, minimum, and maximum) by treatment will be used for the continuous key secondary endpoints.

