6.5. Changes From Protocol-Specified Efficacy Analyses

Due to study termination and insufficient number of subjects enrolled, graphical approach of multiple test procedures will not be implemented, and only the nominal p values will be presented.

Due to small number of subjects available, for key secondary binary endpoints, logistic regression analyses may not be applicable. In such cases, no p-value will be provided. For key secondary continuous endpoints, MMRM analyses may not be applicable. In such cases, only descriptive summary statistics will be provided.

No sensitivity analyses will be performed.

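### The fallback from the MMRM goes straight to by-arm descriptive statistics, with no objective trigger and no simpler model in between, so continuous key secondary endpoints can lose their treatment difference and CI

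*SAP*

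**What the plan says.** SAP 6.3.2 applies one MMRM to five endpoints: change from baseline in HAQ-DI (Week 12) and in SF-36v2 PCS, LEI, FACIT-Fatigue and LDI (Week 16). LEI is analysed only in subjects with enthesitis at baseline, and LDI only in those with dactylitis. Fixed effects are baseline, the stratification factors, treatment, visit and treatment by visit, with "subject being the random effect" and all four arms in the model. On covariance: "An unstructured variance-covariance matrix will be used". No alternative structure is named. Protocol 8.5.2.2.1 uses the same subject term ("stratification factors as fixed effects and subjects as a random effect in the model will be used") and gives no covariance structure.

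The fallback is triggered by "In case of limited data leading to improper use of MMRM model". What follows is n, mean, SD, median, quartiles and range by treatment. SAP 6.5 repeats it ("In such cases, only descriptive summary statistics will be provided") and adds "No sensitivity analyses will be performed".

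Two neighbouring rules matter:
- SAP 6.1 defines the population-level summary for continuous endpoints as the mean difference between each filgotinib group and the comparator.
- SAP 6.3.2 treats binary key secondary endpoints differently. If the logistic model is not usable, only the p-value is dropped. The rate difference and its 95% CI remain.

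**The concern.** The rule has two outcomes, the most heavily parameterised covariance model or no comparison at all, and the choice between them is left to judgement. Nothing defines too little data or improper use, and nothing says whether the decision is made endpoint by endpoint. It can be made after the fit has been seen.

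The trial stopped at 67 subjects, so the estimate and its interval are the main thing these endpoints can still offer. A covariance matrix that cannot be estimated does not mean that the treatment difference cannot be. Under the current rule the first removes the second.

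The model statement is also ambiguous. If it means a random subject intercept in addition to an unstructured within-subject matrix, it is over-parameterised before sample size enters.

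**Working it through.** **The plan's own sizing figure.** The only power statements concern ACR20. For the 50%-retention test (SAP 1.3), the effect is 0.60 − 0.5×0.52 − 0.5×0.386 = 0.147. SE = √(0.60×0.40/244 + 0.25×0.52×0.48/122 + 0.25×0.386×0.614/244) = 0.04169. At two-sided 0.025 the power is 90.06%, which reproduces the stated 90%. No figure is given for the MMRM endpoints or their subsets.

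**Parameter count for LEI and LDI.** SAP Table 3-4 gives four post-baseline visits. SAP 3.3 reduces region to two levels.
- Fixed effects: intercept 1 + baseline 1 + region 1 + csDMARD/apremilast 1 + treatment 3 + visit 3 + interaction 9 = 19.
- Unstructured covariance: 4×5/2 = 10.
- HAQ-DI (five visits): 23 fixed effects and 15 covariance parameters.
- PCS and FACIT-Fatigue (two visits): 11 and 3.

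**Random effect beside the unstructured matrix.** The marginal covariance is V = σ²J + R, where J is a matrix of ones. With four visits, 1 + 10 = 11 parameters map to the 10 distinct elements of V, and the Jacobian has rank 10. Any change in σ² can be absorbed in R, so one parameter is not identifiable at any sample size.

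**Subset size.** Protocol Appendix 25 puts dactylitis at 16-48% of PsA cases. 0.16×67 = 10.7 and 0.48×67 = 32.2, so about 11 to 32 subjects. At 2:2:1:2 that is about 3 to 9 per filgotinib or placebo arm and 2 to 5 on adalimumab. The documents give no enthesitis prevalence. An assumed 30-75% would give 20 to 50 subjects.

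**Week 16 data.** The number with Week 16 data is not stated. SAP 1.3 says that 13 of 67 entered the LTE, but others may have completed the Main Study. Retention was therefore varied.

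**Simulation.** 40 runs per cell; REML; four visits; arms drawn 2:2:1:2; two binary strata; LEI-like integer scores; within-subject correlation 0.5; monotone dropout. A fit failed if its covariance was singular or the optimiser did not converge. The unstructured fit omitted the redundant random effect. Each cell gives the percentage of runs in which the fit succeeded **and** both filgotinib arms and placebo had Week 16 data, as unstructured / compound symmetry:

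| Subjects | 90% retained | 60% | 35% |
|---|---|---|---|
| 11 | 47 / 88 | 5 / 70 | 3 / 42 |
| 16 | 93 / 93 | 55 / 82 | 5 / 47 |
| 20 | 95 / 95 | 80 / 90 | 23 / 68 |
| 25 | 100 / 100 | 97 / 97 | 60 / 85 |
| 32 | 100 / 100 | 100 / 100 | 78 / 82 |
| 40 | 100 / 100 | 100 / 100 | 90 / 90 |
| 50 | 100 / 100 | 100 / 100 | 100 / 100 |

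The gap within a cell is comparisons lost to the covariance choice. The shortfall of the second figure from 100 is comparisons lost because a compared arm had no Week 16 data. Compound symmetry and AR(1) converged in every one of these runs.

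With skewed, zero-heavy LDI-like scores at n=11, the unstructured fit converged in 25%, 5% and 18% of runs at 90%, 60% and 35% retention. At n=20 it converged in 98% and 88% at 90% and 60%. Larger LDI-like cells were not completed. The Monte Carlo standard error is at most about √(0.25/40) = 8 points.

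**Empty cells.** With 10% dropout per visit, the fixed-effect design itself was rank-deficient in about 47% of data sets at n=11, 23% at n=16 and 3% at n=32. No covariance structure cures that.

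**The case against.** The strongest reply is that little rides on this. All p-values are nominal, the testing graph is dropped, and SAP 6.5 openly says the MMRM may not be usable. Three of the five endpoints use the full FAS, and two of those have only two visits. With two or three subjects per arm, declining a model-based contrast is defensible. A reader could form a crude difference from the tabulated n, mean and SD. The subject wording repeats the protocol's and may only mean that subject defines the repeated-measures block. The simulation shows convergence of simpler structures, not their bias or coverage.

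Much of this stands, and it limits the consequence. It does not supply a trigger. A crude difference worked out by the reader is unadjusted for baseline and is not a planned result. Disclosure also does not explain why binary endpoints keep a difference and CI while continuous ones do not.

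Three stronger readings are tempting and not supported:
- **The MMRM is likely to fail in both subsets.** For dactylitis this holds only near the low end of the range or with poor Week 16 retention. The 16-48% is background text about PsA generally, not an expectation for this trial. The enthesitis subset cannot be sized at all.
- **Any failure is due to the unstructured matrix.** At 16 subjects and 90% retention the two structures do equally well (93 / 93), and the remaining loss comes from arms without Week 16 data.
- **The descriptive fallback uses only completers.** SAP 6.1 keeps all available Main Study data, including data after drug discontinuation. Anyone observed at a visit counts at that visit.

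**Conclusion.** The point stands as a defect in the fallback rule: one unstructured MMRM, an undefined trigger, then no between-group estimate. The MMRM may fail, depending on subset size and Week 16 retention. Near 11 subjects the unstructured fit gave a usable Week 16 comparison in 47% of LEI-like runs at best and 3% at worst, against 88% and 42% with compound symmetry. At about 25 or more subjects with at least 60% retention, the covariance choice cost nothing in the simulation. These figures rest on assumed score distributions, correlation and retention. The 25-subject mark comes from LEI-like scores only and is less certain for LDI.

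The random-effect redundancy is exact on a literal reading and affects all five MMRM endpoints. On the other reading it needs only a clarifying phrase.

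The change is worth making. No confirmatory claim depends on it; what is at stake is whether a terminated trial reports the estimates it can support.

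**What to change.** In SAP 6.3.2 and 6.5:
1. Drop the separate random effect, or state that subject defines the repeated-measures block.
2. Define non-convergence objectively (for example, optimiser failure or a singular covariance estimate) and apply it per endpoint.
3. Pre-specify the order: unstructured; heterogeneous Toeplitz; AR(1) or compound symmetry; then ANCOVA at the target visit with baseline and treatment, omitting empty arms. Report the difference and 95% CI at whichever step is reached.
4. Use descriptive statistics alone only when a compared arm has fewer than a stated minimum number of observed subjects.

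The cost is a few lines. If the SAP is already final, SAP section 1 provides for documenting the change in the CSR. The downside is that simpler structures assume more about the correlation, and ANCOVA uses only subjects observed at that visit, so the step reached should be reported with each estimate.

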6.4. Other Secondary Efficacy Endpoint

Other secondary endpoints will be evaluated at all scheduled or applicable time points in the Main Study other than the time points that are already specified in the primary and key secondary endpoints.

CCI

The other secondary endpoints include:

- Change from Baseline in PASDAS

- MDA response
- VLDA response
- Change from Baseline in DAPSA
- Change from Baseline in PhGAP, in subjects with psoriasis covering $\geq 3\%$ of the BSA at Baseline
- Change from Baseline in mNAPSI, in subjects with psoriatic nail involvement at Baseline
- Change from Baseline in LEI, in subjects with enthesitis at Baseline
- Change from Baseline in PsAID-12
- PASDAS low disease activity (LDA, i.e. PASDAS ≤ 3.2)
- PASDAS remission (i.e. PASDAS ≤ 1.9)
- ACR20 response
- ACR50 response
- ACR70 response
- Change from Baseline in individual components of the ACR response criteria
- Change from Baseline in DAS28(CRP)
- DAS28(CRP) LDA
- DAS28(CRP) remission
- Time to achieve DAS28(CRP) LDA
- DAPSA LDA
- DAPSA remission
- Time to achieve DAPSA LDA
- PsARC response
- Change from Baseline in PASI, in subjects with psoriasis covering $\geq 3\%$ of the BSA at Baseline
- PASI50 response, in subjects with psoriasis covering $\geq 3\%$ of the BSA at Baseline
- PASI75 response, in subjects with psoriasis covering $\geq 3\%$ of the BSA at Baseline

- PASI90 response, in subjects with psoriasis covering $\geq 3\%$ of the BSA at Baseline
- PASI100 response, in subjects with psoriasis covering $\geq 3\%$ of the BSA at Baseline
- Change from Baseline in SPARCC Enthesitis Index, in subjects with enthesitis at Baseline
- Change from Baseline in LDI, in subjects with dactylitis at Baseline
- Change from Baseline in tender dactylitis count (TDC), in subjects with dactylitis at Baseline
- Change from Baseline in HAQ-DI
- Change from Baseline in FACIT-Fatigue
- Change from Baseline in SF-36v2 PCS and mental component score (MCS)

6.4.1. Definition of Other Secondary Endpoints

6.4.1.1. Tender Dactylitis Count (TDC)

Tender score (0 = no tenderness, 1 = tender, 2 = tender and wince, 3 = tender and withdraw) is collected for Dactylitis Assessments on the Dactylitis Score Sheet that was used for calculation of LDI total score.

Tender dactylitis count (TDC) equals the number of tender fingers and toes (tender score >0). For subjects with dactylitis status absent for all the fingers and toes, the TDC will be set as 0. This score is used as a component of the PASDAS.

If there are missing fingers or toes, then the missing count for those fingers or toes will not be included in the TDC.

6.4.1.2. Psoriatic Arthritis Disease Activity Score (PASDAS), PASDAS Low Disease Activity (LDA) and PASDAS remission

$$\text{PASDAS} = \left[0.18 \times \sqrt{\text{PhGADA}} + 0.159 \times \sqrt{\text{PGADA}} - 0.253 \times \sqrt{\text{PCS}} + 0.101 \times \ln(\text{SJC66} + 1) + 0.048 \times \ln(\text{TJC68} + 1) + 0.23 \times \ln(\text{LEI} + 1) + 0.377 \times \ln(\text{TDC} + 1) + 0.102 \times \ln(\text{CRP} + 1) + 2 \right] \times 1.5$$

where

PhGADA = Physician's Global Assessment of Disease Activity (0 – 100 VAS);

PGADA = Patient's Global Assessment of Disease Activity (0 – 100 VAS);

PCS = Physical Component Score of the SF-36;

LEI = Leeds Enthesitis Index, derived from the enthesitis assessments;

TDC = Tender Dactylitis Count from the LDI;

CRP is in the unit of mg/L.

A lower score indicates better function.

If a subject did not have dactylitis at baseline and hence no dactylitis assessments are collected post-baseline, then it is assumed that TDC = 0 at baseline and all post-baseline visits for calculating PASDAS.

If a subject did not have enthesitis at baseline and hence no enthesitis assessments are collected post-baseline, then it is assumed that LEI = 0 at baseline and all post-baseline visits for calculating PASDAS.

If any of the components is missing, then PASDAS remains missing.

PASDAS LDA is defined as $PASDAS \leq 3.2$; PASDAS remission is defined as $PASDAS \leq 1.9$.

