6.6.3.3. Independent Assessor

Assessment of tender and swollen joints, dactylitis, enthesitis, and psoriasis of the skin and nails will take place at the time points indicated in the Study Procedures Table ([Appendix 2](#)). The clinical assessment forms are provided in [Appendix 20](#), [Appendix 21](#), [Appendix 23](#), [Appendix 24](#), and [Appendix 25](#).

An independent clinical assessor with adequate training including completion of the required training provided by the Sponsor, and experience in performing these assessments will be designated at each study site to perform all relevant assessments including SJC66 / TJC68, SPARCC Enthesitis Index and LEI, LDI, PASI including BSA, and mNAPSI should be blinded to the other study assessments performed on that day. The assessor should preferably be a rheumatologist; however, if a rheumatologist is not available, it should be a health care worker who has completed the required training provided by the Sponsor and has experience in performing these assessments. The assessor should remain the same throughout the study per subject, as much as possible. It is required that the designated assessor identify an appropriate back up assessor to provide coverage if the designated assessor is absent.

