Appendix 2. Study Procedures Table

EVENT		Part 1: Main Study								
		Screen (-28 days to 0)	Day 1	Weeks (±3 days)					ET (±7 days)	Safety Follow-up (±7 days) ^a
				2	4	8	12	16		
Visit (±window)										
Screening Assessments	Informed consent	X								
	Inclusion / Exclusion Criteria	X	X ^b							
	Demographics, Baseline / Disease Characteristics, PsA Diagnosis and Prior PsA Treatment, Medical History	X								
	Complete Physical Examination	X								
	TB Screening and Chest X-ray	X								
Patient Reported Outcomes	HAQ-DI: Health Assessment Questionnaire – Disability Index		X	X	X	X	X	X	X	
	FACIT-Fatigue: Functional Assessment of Chronic Illness Therapy – Fatigue Scale		X		X			X	X	
	SF-36v2: 36-item Short-Form Health Survey Version 2		X		X			X	X	
	PsAID-12: 12-item Psoriatic Arthritis Impact of Disease		X		X			X	X	
	CCI									
	CCI									
	CCI									
	CCI									
	PGADA: Patient’s Global Assessment of Disease Activity		X	X	X	X	X	X	X	
	PGAPI: Patient's Global Assessment of Psoriatic Arthritis Pain Intensity		X	X	X	X	X	X	X	

EVENT		Part 1: Main Study								
		Screen (-28 days to 0)	Day 1	Weeks (±3 days)					ET (±7 days)	Safety Follow-up (±7 days) ^a
				2	4	8	12	16		
Visit (±window)										
Physician Reported Outcomes	CASPAR: Classification Criteria for Psoriatic Arthritis	X								
	PASI including BSA: Psoriasis Area and Severity Index including Body Surface Area		X		X	X	X	X	X	
	mNAPSI: Modified Nail Psoriasis Severity Index		X		X	X	X	X	X	
	PhGAP: Physician's Global Assessment of Psoriasis		X	X	X	X	X	X	X	
	SPARCC Enthesitis Index and LEI: Spondyloarthritis Research Consortium of Canada Enthesitis Index and Leeds Enthesitis Index		X		X	X	X	X	X	
	SJC66 / TJC68: Swollen and Tender Joint Count	X	X	X	X	X	X	X	X	
	LDI: Leeds Dactylitis Index		X		X	X	X	X	X	
	PhGADA: Physician's Global Assessment of Disease Activity		X	X	X	X	X	X	X	
Safety	Vital Signs and Weight	X	X	X	X	X	X	X	X	
	Symptom-Driven Physical Examination		X	X	X	X	X	X	X	
	12-Lead ECG	X								
	Pregnancy Test ^c	X	X	X	X	X	X	X	X	X

EVENT		Part 1: Main Study								
		Screen (-28 days to 0)	Day 1	Weeks (±3 days)					ET (±7 days)	Safety Follow-up (±7 days) ^a
				2	4	8	12	16		
Visit (±window)										
Laboratory	Hematology and Chemistry	X	X	X	X	X	X	X	X	
	Urinalysis	X								
	Endocrine: FSH, TSH, and HbA1c ^d	X								
	Lipid profile (fasting)		X					X	X ^e	
	Serum CRP ^f		X	X	X	X	X	X	X	
	CCI									
	CCI									
	CCI									
	Biomarker Samples ^f		X	X	X		X	X		
	Viral Serology ^j	X								

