Appendix 21. mNAPSI: Modified Nail Psoriasis Severity Index

Modified Nail Psoriasis Severity Index (mNAPSI)

mNAPSI will be collected only in subjects with psoriatic nail involvement. This tool will ask you to assess each nail abnormality for each of a subject's nails. If you question which grade to give, your answer should be the lower of the grades. Three features or groups of features (pitting, onycholysis together with oil-drop dyschromia, and crumbling) of each fingernail will be graded on a scale from zero to 3, according to the directions below. Four features (leukonychia, splinter hemorrhages, hyperkeratosis, and red spots in the lunula) will be graded as either present or absent for each fingernail.

1. Onycholysis: Separation of the nail plate from the nail bed. The separated part of the nail is opaque and can have white, yellow, or greenish tinge. If there is a piece of nail missing, estimate where the nail normally would have ended at the end of the nail bed, and count that missing part as involved in onycholysis.

Oil-drop (salmon patch) dyschromia: Reddish-brown discoloration under the nail plate.

Onycholysis and oil-drop dyschromia are considered together. When looking at the nail, combine the total percentage area of the nail that is affected by either and use that combined total to score the nail.

Score: Percent of nail with onycholysis or oil-drop dyschromia present

- 0 No onycholysis or oil drop dyschromia present
- 1 1–10% of the nail has onycholysis or oil-drop dyschromia
- 2 11–30% of the nail has onycholysis or oil-drop dyschromia
- 3 >30% of the nail has onycholysis or oil-drop dyschromia

2. Pitting: Small, sharply defined depressions in the nail surface. Pits are discrete abnormalities ("icepick-like"). If there is nail plate crumbling that is confluent with pits, do not score for pits. If the pits are separate from crumbling, they may be scored regardless of whether crumbling is present or not.

Score: Number of pits

- 0 0
- 1 1–10
- 2 11–49
- 3 ≥ 50

3. Nail plate crumbling: Crumbling or fragmentation of friable nail plate which may be associated with confluent pitting. Crumbling involves alteration of the nail plate surface. Horizontal ridging of the nail, "wave-like" appearance, and horizontal lines are all features of crumbling.

Score: Percent of nail with crumbling present

- 0 No crumbling
- 1 1-25% of the nail has crumbling
- 2 26-50% of the nail has crumbling
- 3 > 50% of the nail has crumbling

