6.3.1.5. Minimal Disease Activity (MDA)

MDA is a measure to indicate disease remission, and is based on a composite score of 7 domains.

A subject will be classified as having achieved MDA when at least 5 out of 7 of the following criteria are met.

- TJC68 ≤ 1,
- SJC66 ≤ 1,

- $PASI \leq 1$ for subjects with a Baseline psoriasis covering at least 3% of the BSA (or for subjects with a Baseline psoriasis covering $BSA < 3\%$, this criterion is considered met),
- Patent’s Global Assessment of PsA pain intensity (PGAPI) score ≤ 15 (0 – 100 VAS),
- $PGADA \leq 20$ (0 – 100 VAS),
- $HAQ-DI \leq 0.5$,
- Leeds Enthesitis Index ≤ 1 for subjects with enthesitis at Baseline (or for subjects without enthesitis at Baseline, this criterion is considered met).

In the case that some of the MDA components are missing, the MDA assessment will be based on the nonmissing components. If nonmissing components are not sufficient to determine the MDA response, then the MDA response will be considered as missing.

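### SAP 6.4.1.2 and 6.3.1.5 let baseline status stand in for recorded dactylitis and enthesitis in PASDAS, MDA and VLDA, although the protocol schedules both assessments for every subject

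*SAP*

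**What the plan says.** **SAP 6.4.1.2 (PASDAS).** The dactylitis rule opens with a subject who had no dactylitis at baseline and continues: "hence no dactylitis assessments are collected post-baseline, then it is assumed that TDC = 0 at baseline and all post-baseline visits". The enthesitis rule has the same form: "hence no enthesitis assessments are collected post-baseline, then it is assumed that LEI = 0 at baseline and all post-baseline visits". The same section leaves PASDAS missing if any component is missing.

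**SAP 6.4.1.1 (TDC).** TDC is already 0 when dactylitis is recorded as absent in all digits.

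**SAP 6.1.** Composites are built, unless otherwise specified, from the component data selected in each analysis window. The treatment policy estimand takes in all on-study data.

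**SAP 6.3.1.5 (MDA).** The enthesitis criterion is LEI of 1 or less, but "for subjects without enthesitis at Baseline, this criterion is considered met". SAP 6.4.1.3 uses the same seven criteria for VLDA and requires all of them.

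**Protocol.** Section 6 says Appendix 2 gives the procedures for each enrolled subject. Section 6.6.3.3 states: "Assessment of tender and swollen joints, dactylitis, enthesitis, and psoriasis of the skin and nails will take place at the time points indicated". In Appendix 2 the rows for SPARCC/LEI and "LDI: Leeds Dactylitis Index" are marked at Day 1, Weeks 4, 8, 12 and 16 and early termination, and continue in the extension. No footnote restricts them. Appendix 21 does restrict one instrument: "mNAPSI will be collected only in subjects with psoriatic nail involvement".

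**The concern.** The SAP treats non-collection as a consequence of baseline status, but nothing in the protocol makes it one. A programmer who takes the SAP sentence at face value would set TDC or LEI to 0 at every visit in a subject unaffected at baseline, whatever the assessor recorded.

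The resulting error runs one way. It can only lower PASDAS, and only in subjects who develop new disease, so its product is subjects counted in low disease activity or remission who are not.

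The MDA rule raises the same issue without any statement about collection. It depends on baseline status alone, so a recorded Week 16 LEI of 2 or more is ignored. MDA at Week 16 is a key secondary endpoint.

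**Working it through.** The plan states no figure on this point, so there is none to reproduce. The check is a comparison of texts followed by arithmetic from the SAP formula.

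**1. Is collection limited by baseline status?** The phrase restricting analyses to subjects with enthesitis or dactylitis at baseline (Protocol 3.1.2 and 3.1.3; SAP 6.3.1.3 and 6.3.1.7) defines who is analysed for LEI and LDI. It does not say who is examined. PASDAS carries no such restriction. Appendix 25 has the examiner inspect fingers and toes and measure those that look dactylitic, which can detect new disease. Neither Appendix 23 (enthesitis) nor Appendix 25 (dactylitis) carries a restriction like the one in Appendix 21.

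**2. What does a forced 0 remove from PASDAS?** From SAP 6.4.1.2, the two terms sit inside a bracket multiplied by 1.5:

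- TDC: 1.5 × 0.377 × ln(TDC + 1)
- LEI: 1.5 × 0.23 × ln(LEI + 1)

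| Recorded count | TDC set to 0 removes | LEI set to 0 removes |
|---|---|---|
| 1 | 0.392 | 0.239 |
| 2 | 0.621 | 0.379 |
| 3 | 0.784 | 0.478 |

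One tender digit plus one LEI site: 0.392 + 0.239 = 0.631.

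**3. Which subjects change status?** The cut-offs are 3.2 (low disease activity) and 1.9 (remission). With one suppressed tender digit, any true score above 3.2 and up to 3.2 + 0.392 = 3.592 is counted as low disease activity, and any score above 1.9 and up to 1.9 + 0.392 = 2.292 as remission. With one suppressed LEI site the upper limits are 3.439 and 2.139.

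**4. Two illustrations (component values assumed).**

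- PhGADA 20, PGADA 20, PCS 45, SJC66 1, TJC68 2, CRP 3 mg/L. With TDC = LEI = 0, PASDAS is 3.125, so low disease activity is met. With TDC 1 it is 3.517, with LEI 1 it is 3.364, and with both it is 3.756. None of these three meets it.
- PhGADA 5, PGADA 5, PCS 50, joint counts 0, CRP 1 mg/L. PASDAS is 1.560 (remission) with TDC 0 and 1.952 (not remission) with TDC 1.

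**5. When do MDA and VLDA change?** MDA needs 5 of 7 criteria. The credit matters when a subject unaffected at baseline has LEI of 2 or more and meets exactly 4 of the other 6. For VLDA it matters when that subject meets all of the other 6.

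**6. Group level.** The rate of new dactylitis or enthesitis is not in the documents. For TDC only, assume new single-digit tender dactylitis in a fraction a of unaffected placebo subjects and b of unaffected filgotinib subjects, with a share f of subjects unaffected at baseline. The shift in the mean difference is f × (a − b) × 0.392. Appendix 25 cites dactylitis in 16–48% of PsA as general background, giving f = 0.52–0.84.

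- a = 0.05, b = 0.02, f = 0.52: 0.52 × 0.03 × 0.392 = 0.006
- a = 0.15, b = 0.05, f = 0.84: 0.84 × 0.10 × 0.392 = 0.033

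On these assumptions the shift is about 0.01 to 0.03 PASDAS points.

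**The case against.** **The PASDAS sentence may be conditional.** Its antecedent joins no disease at baseline with no later assessments. Read strictly, the rule does not fire when an assessment exists, and recorded values would count. That reading is available. But the sentence presents non-collection as following from baseline status and applies the 0 to all later visits, so the broader reading is the natural one. Even the strict reading leaves a premise that contradicts the protocol.

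**A schedule row does not prove collection.** The mNAPSI row in Appendix 2 is as unrestricted as the LEI and LDI rows, yet Appendix 21 restricts mNAPSI. The SAP is also based on the eCRF, which is not available here. If the electronic form skipped unaffected subjects, no recorded value is lost. This stands as a limit on what can be claimed.

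**A rule for uncollected data has a purpose.** SAP 6.4.1.1 covers recorded absence only. Without a further rule, unaffected subjects with no assessment would have PASDAS missing. This is fair, and the fix provides for it. Likewise, SAP 6.1 allows exceptions to its general steps, so the rule is not in itself a breach of them.

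**The MDA rule resembles the PASI criterion.** In the same list, the PASI criterion is credited below 3% BSA. There, though, SAP 6.3.1.4 gives a measurement reason: the score is considered unreliable at that extent. No such reason is given for LEI.

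**The stakes are low.** PASDAS is an other secondary endpoint, with change summarised descriptively and response given as observed rates and differences with confidence intervals. PCS is scheduled only at Day 1, Week 4 and Week 16 in the Main Study, so post-baseline PASDAS exists at two Main Study visits. The study stopped at 67 subjects and all p-values are nominal. All of this stands.

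**Conclusion.** The concern holds in limited form. The SAP's premise about collection does not match the protocol. On its natural reading, the PASDAS rule replaces recorded new disease with 0, at a cost of 0.39 points for one tender digit and 0.24 for one LEI site. That is enough to change low disease activity or remission status near the cut-offs. The MDA and VLDA credit disregards a recorded LEI of 2 or more on any reading.

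A reader might infer three stronger things that the documents do not support:

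- *That recorded findings were certainly erased.* This depends on how the sentence is read and on whether the eCRF collected the data.
- *That most subjects are mis-scored because most lack dactylitis at baseline.* Zero is correct for everyone who stays unaffected; only those with new disease are affected.
- *That the treatment comparison is materially biased.* The incidence rates needed are not in the documents. Under the assumed rates the mean PASDAS difference moves by only about 0.01 to 0.03, and if new disease is more frequent on placebo the shift dilutes the filgotinib effect. No count of changed MDA or VLDA classifications can be derived.

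The change is worth making because it is nearly free and removes an error that can only flatter response.

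**What to change.** 1. In SAP 6.4.1.2, delete the premise that unaffected subjects have no later assessments. State that the TDC and LEI recorded in each analysis window are used for all subjects, and that either is set to 0 only when the visit record shows absence.
2. In SAP 6.3.1.5, and through it 6.4.1.3, judge the enthesitis criterion on recorded LEI of 1 or less for all subjects.
3. Where no assessment was recorded, apply the existing rules: PASDAS missing, and MDA and VLDA from the nonmissing components. A default of 0, or a default credit, at any unrecorded visit should be avoided. It would score missed examinations as disease-free in a study where SAP 4.4 describes visits missed because of COVID-19.
4. If the eCRF by design did not collect these data in unaffected subjects, say so, keep the zero assumption only for visits otherwise attended, and flag it as an assumption.

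The cost is SAP wording and a small derivation change. As the SAP is already signed, SAP section 1 calls for documenting the change in the study report. Expect slightly fewer PASDAS low disease activity, PASDAS remission, MDA and VLDA responders, and a few more missing PASDAS values.
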